### **10.1.7 Tapping**

**BACKGROUND:** Performance of individuals with HD on finger or hand tapping tasks is shown to be highly correlated with various indices of disease severity and is a sensitive marker of change over time (4). Additionally, measures of tapping performance are strongly related to estimated-years-to-onset in pre-motor manifest HD (5).

**AIM:** To investigate cross-sectional and longitudinal sensitivity of a finger/hand-tapping task, as a measure of cognitive change across different stages of HD, including pre-motor manifest HD.

**STUDY POPULATION:** Confirmed HD mutation carriers of all stages of the disease, including Pre-HD.

**ASSESSMENT BATTERY:** Task selection and device will be determined following systematic review of all tapping tasks so far employed in HD. The task will measure motor speed, dexterity and psychomotor speed.

**ASSESSMENT:** approximately 5 minutes

**METHODOLOGICAL APPROACH:** This device and task instructions will be distributed to multiple study sites and should be administered to confirmed HD gene mutation carriers of all stages of the disease.

**OUTCOMES:** Tapping performance appears to be a sensitive readout for both pre-motor manifest HD mutation carriers as well as manifest HD patients well into more advanced stages of HD. This sub-study will select a task with proven sensitivity to detect and track changes within HD across all stages will be tested for task robustness. These data will be use used specifically to assess task robustness within multiple study sites and confirm whether this device should be employed in the future, e.g. in the context of the Enroll-HD assessment battery and in the context of clinical trials.

#### **10.1.8 HD Quality of Life outcome measure (carer, patient)**

**BACKGROUND:** Previous work in health related quality of life in HD (6) shows that while generic instruments may be applied in HD patients, these may not fully capture the aspects of well-being affected specifically in HD. Generic instruments tend to demonstrate poor sensitivity to specific disease progression because they often fail to capture all aspects of well-being. Specifically, the SF-36 lacks items tapping into the relevant mood-related (7) and behavioural (8) aspects of Huntington's disease which affect health-related quality of life. The health-related quality of life (HrQoL) in HD is a new questionnaire meeting with psychometric standards and will be the first ever HD-specific quality of life instrument. This measure will enable the unique symptoms and consequences of this disorder on patients' everyday life to be formally ascertained and quantified, and will fill a long-standing practical gap in current clinical care and management of this disorder. An HD specific health-related quality of life questionnaire would therefore be extremely useful in understanding both the impact of disease progression and intervention on health status.

**AIM:** To develop and validate a patient-centred prototype questionnaire which examines health-related quality of life specifically in people with Huntington' disease, and to validate this instrument as an outcome measure to reflect a combination of factors: a person's health, symptoms, and level of physical and social functioning.

**STUDY POPULATION:** All Enroll-HD participants, including pre-manifest HD and at risk individuals.

ASSESSMENT:

- a. HD QoL: Self-rated by participant, and proxy-version completed by carer/companion
- b. Companion QoL survey
- c. EuroQuol 5, a non-specific quality of life questionnaire.

ASSESSMENT DURATION: 20 minutes each.

**METHODOLOGICAL APPROACH:** The development of the HD QoL scales falls into two stages. During Stage I (in progress and coordinated outside of Enroll-HD), data will be explored to gauge the suitability of conducting an exploratory factor analysis. It is anticipated that the majority of items will demonstrate a normal distribution using the Kalmogorof Smirnov test. The screened data will be factor analyzed to establish the underlying dimensions of the instrument. Principal components analysis (PCA) will be used and it is expected to find factors which can be clinically interpretable and to fall under the triad of underlying motor, cognitive and behavioural factors consistent with the typical presentation of HD. Any factors which appear clinically heterogeneous will undergo a further PCA to determine if there is a basis for establishing separate factors.

The psychometric characteristics of the factors will be examined including missing data, score distribution, summary scores, floor and ceiling effects, internal consistency (expressed as part-whole correlations between single items with the scale value) and reliability of the total scale (using Chronbach's alpha coefficient). The analyses of these data involve iterative changes to the questionnaire.

Once the HDQoL has been finalised, Stage 2 (the aim of this sub-study) will commence to establish the HDQoL as a valid, reliable and sensitive instrument in tracking the progression of disease. A target figure of 300 HD patients is required to participate in this validation study.

Patients will be asked to rate their duration of disease and their level of independence in daily life. Convergent validity can be determined by examining the correlations between the factors from the HDQoL instrument with other disease characteristics (such as functional motor impairment and cognitive status) and other QoL measures. Multivariate regression models can be used to examine the discriminative and evaluative properties of the HDQoL, as can known-groups validation.

In order to examine reliability of the instrument over time, after approximately 4 weeks from the receipt of the initial questionnaires, a second send-out will occur. Internal

consistency will be examined using Chronbach's alpha coefficient, and test-retest reliability using intraclass correlation coefficients.

In order to determine the sensitivity of the instrument to progression in disease state, a final send out of the HDQoL instrument (as per the initial Time 1 send out and post send-out interview) will be administered 12 to 18 months after the receipt of the initial questionnaire. Changes in HDQoL factors will be correlated with changes with motor, cognitive and behavioural disease symptoms. Standardized response means, effect sizes and ROC curves will also be used to determine sensitivity of the instrument.

Finally, in order to assist in interpreting scores over the progression of the disease, it would be important to determine minimally important changes i.e. the smallest (positive or negative) difference in scores that patients perceive as important. This will be done using anchor and distribution based methods.

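### Stage I of the HDQoL development expresses factor internal consistency as correlations of items with a scale value that, as worded, contains the item, which inflates the result in short factors

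*Protocol*

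**What the plan says.** Protocol section 10.1.8, under the methodological approach, splits the development of the HDQoL into two stages (development stages, not disease stages).

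- **Stage I.** "During Stage I (in progress and coordinated outside of Enroll-HD), data will be explored", and a factor analysis follows: "Principal components analysis (PCA) will be used and it is expected to find factors which can be clinically interpretable". Factors that look clinically mixed go through a further PCA. Then "The psychometric characteristics of the factors will be examined including missing data, score distribution, summary scores". The list also covers effects at the floor and ceiling of the scores. For agreement among the items it specifies "internal consistency (expressed as part-whole correlations between single items with the scale value"). As a separate entry it plans "reliability of the total scale (using Chronbach's alpha coefficient"). The paragraph closes: "The analyses of these data involve iterative changes to the questionnaire".
- **Stage 2.** This begins once the questionnaire is final, and the section identifies it as the sub-study's aim. Here internal "consistency will be examined using Chronbach's alpha coefficient, and test-retest reliability using intraclass correlation coefficients". The sample size is given: "A target figure of 300 HD patients is required to participate in this validation study".

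The section gives no number of items per factor, no Stage I sample size, no threshold for keeping or dropping an item, and no mention of removing the item from the scale value before correlating.

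**The concern.** A correlation between an item and a total that contains the item has a built-in positive component. Even when the item shares nothing with the rest of the scale, it shares its own variance with the total. The fewer the items, the larger that share. The usual remedy is to correlate the item with the sum of the other items (the item-rest, or corrected item-total, correlation).

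The protocol names the statistic and says what is correlated with what, so this is more than a detail left open. It is also the only item-level consistency check named after the factors are formed; alpha in Stage I is named for the total scale. The results sit among the analyses that lead to changes in the questionnaire, and Stage 2 validates whatever comes out. If a factor is short, an item that does not belong can look acceptable, and the sub-scale can look more coherent than it is.

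**Working it through.** **Inputs from the protocol (section 10.1.8).** The item-to-scale correlation as worded, its use at factor level, its place in Stage I, and alpha for the total scale. The protocol states no figure for this point, so there is nothing to reproduce.

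**Assumptions.** Items of unit variance, summed with equal weight; *m* items per factor (not given, so a range is shown); inter-item correlation *r* = 0.3 for items that belong together (not given), with 0.5 as a sensitivity value. The scale value is taken to be that of the item's own factor, because the sentence lists characteristics of the factors.

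**1. All *m* items mutually unrelated.** The covariance of an item with the total is 1 and the variance of the total is *m*, so part-whole correlation = 1/√*m*. The item-rest correlation is 0, and so is alpha.

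| *m* | 3 | 5 | 10 | 20 | 40 |
|---|---|---|---|---|---|
| part-whole | 0.58 | 0.45 | 0.32 | 0.22 | 0.16 |
| item-rest | 0 | 0 | 0 | 0 | 0 |

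**2. One unrelated item among *k* = *m* − 1 items that correlate *r* = 0.3.** The variance of the total is V = 1 + *k* + *k*(*k* − 1)*r*. The part-whole correlation is 1/√V for the unrelated item and (1 + (*k* − 1)*r*)/√V for each related item. The item-rest correlation of the unrelated item is 0.

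| *m* | V | unrelated item, part-whole | related item, part-whole |
|---|---|---|---|
| 3 | 1 + 2 + 0.6 = 3.6 | 1/√3.6 = 0.53 | 1.3/√3.6 = 0.69 |
| 5 | 1 + 4 + 3.6 = 8.6 | 1/√8.6 = 0.34 | 1.9/√8.6 = 0.65 |
| 6 | 1 + 5 + 6 = 12 | 1/√12 = 0.29 | 2.2/√12 = 0.64 |
| 10 | 1 + 9 + 21.6 = 31.6 | 1/√31.6 = 0.18 | 3.4/√31.6 = 0.60 |

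With *r* = 0.5 the unrelated item shows 0.38 at *m* = 4, 0.25 at *m* = 6 and 0.15 at *m* = 10.

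**3. All items belong, common correlation 0.3.** Part-whole = √((1 + (*m* − 1)*r*)/*m*); item-rest = (*m* − 1)*r*/√((*m* − 1)(1 + (*m* − 2)*r*)).

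- *m* = 3: √(1.6/3) = 0.73 against 0.6/√2.6 = 0.37.
- *m* = 5: √(2.2/5) = 0.66 against 1.2/√7.6 = 0.44.
- *m* = 10: √(3.7/10) = 0.61 against 2.7/√30.6 = 0.49.

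The part-whole value falls as the factor lengthens, while the item-rest value rises.

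**4. Sampling check.** In 2,000 simulated samples of wholly unrelated items with an assumed n = 300 (300 is the Stage 2 target; the Stage I size is not given), the part-whole correlation exceeded 0.30 in 100% of samples at *m* = 4, 98% at 6, 61% at 10, 7% at 20 and 0.6% at 40. The item-rest correlation never did. The 0.30 is illustrative and does not come from the protocol.

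**5. Would alpha catch it?** With *r* = 0.3, alpha with and without one unrelated item is 0.41 against 0.56 (*m* = 4), 0.60 against 0.68 (*m* = 6) and 0.76 against 0.79 (*m* = 10). Alpha for a single factor does respond, most clearly when the factor is short. In Stage I, however, the section names alpha for the total scale only, and alpha-if-item-deleted is not mentioned.

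**The case against.** The strongest reply has four parts.

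- **The step is outside the sub-study.** Stage I is run elsewhere, and Stage 2 uses alpha. This stands, and it limits the point. A reader might infer that the sub-study's own internal-consistency analysis is faulty; the text does not support that. Stage I still matters here because the protocol makes its product the instrument that Stage 2 validates.
- **The appendix is an outline.** Section 5.4.7 promises each sub-study its own protocol and data analysis plan, and an overlap correction could be specified there or already be in use. The possibility is real, and the fix allows for it. But the outline does more than stay silent: it names a statistic whose plain meaning includes the item.
- **Nothing says this correlation decides items.** No cut-off is stated; PCA comes first, and alpha, score distributions and missing data are also examined. A reader might infer that unrelated items will be retained. The documents show only that they could be. An unrelated item also still ranks lowest: 0.34 against 0.65 with 5 items, and 0.18 against 0.60 with 10.
- **Short factors are not shown.** A further PCA only asks whether there is a basis for separate factors, and no item counts are given. This also stands. If the factors are long, or if the scale value means the total score, the inflation is small.

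Two further readings go too far. One is that the statistic does not measure internal consistency at all: by the third formula above it rises with *r*, so it tracks consistency with an upward offset. The other is that the instrument's ability to follow progression is damaged: no figure supports this, and Stage 2 tests responsiveness directly with correlations of change, standardized response means, effect sizes and ROC curves.

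**Conclusion.** The point holds for Stage I only, at low severity. As worded, the item-to-scale correlation is inflated by the item's own contribution. For factors of 3 to 5 items the inflation is material: 0.58 to 0.45 where the true item-rest value is 0 for every item, and 0.53 to 0.34 for a single unrelated item among items correlating 0.3. At 6 items the single unrelated item shows 0.29, and at 10 it shows 0.18, by which length it is easy to tell from the others. These figures rest on equal weights, unit variances and assumed factor lengths and correlations. Whether any item was or will be wrongly kept cannot be determined from the protocol. Stage 2 is not affected by this defect, although its alpha comes after the items have been chosen and so does not guide that choice.

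**What to change.** In section 10.1.8, replace the part-whole phrase with corrected item-rest correlations (each item against the sum of the other items in its factor), and add alpha-if-item-deleted for each factor beside the alpha for the total scale. If Stage I has used uncorrected values, recompute them on the data already collected before the questionnaire is finalised. If Stage I has already used the corrected form, say so in the text; nothing further is then needed.

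The cost is a change of wording and, at most, a re-run on existing data, with no new participants. The reported item correlations will be lower than the uncorrected ones, for example 0.44 instead of 0.66 for a 5-item factor whose items correlate 0.3, and any threshold in use should be read on the corrected scale.

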#### **10.1.9 Physiotherapy outcome measures**

**BACKGROUND:** An evidence-based rationale for the development and evaluation of complex physiotherapy interventions is required to confirm the common perception that physiotherapy is beneficial in HD.

**AIM:** To evaluate a range of physiotherapy related outcome measures for use in future interventional studies.

**STUDY POPULATION:** Either a confirmed diagnosis of HD or HD gene mutation carrier.

#### **ASSESSMENT BATTERY:**

- a. The 6-Minute Walk test.
- b. The 10m Walk test
- c. The timed "Up and Go".
- d. Physical Performance Test
- e. Rivermead Mobility Index
- f. Barthel Index
- g. Berg Balance Scale
- h. Romberg and Sharpened Romberg Test
- i. Performance Oriented Mobility Assessment
- j. Four square step test
- k. International Physical Activity Questionnaire

**ASSESSMENT DURATION:** 60-90 minutes, two visits (one week apart). This study will be coordinated by the Physiotherapy Working Group Lead Facilitators.

**METHODOLOGICAL APPROACH:** Eighty participants with Huntington's disease; 20 pre-HD (TFC 13; no clinical signs of HD); 20 Stage I HD (TFC 10-13); 20 Stage II HD (TFC 7-9); 20 Stages III and IV (TFC 0-6). Twenty participants (tested twice) in each stage of disease would be sufficient to identify an intraclass correlation coefficient of .75, as well as a Pearson's correlation of .6 (two-tailed), with a power of 80% and an alpha of .05.

**OUTCOMES:** Reliability will be assessed using the Intra class correlation coefficient. Validity will be assessed using a Pearson's or Spearman's correlation coefficient correlating functional outcome measures with UHDRS Motor score and Functional Assessment scale for each subject. Minimal Detectable Change (MDC) will be calculated as  $1.96 * \sqrt{2} * SEM$  (standard error of measurement). SEM will be estimated by taking the square root of the mean error term from a repeated measures ANOVA. The MDC can be interpreted as the magnitude of change below which there is more than a 95% chance that no real change has occurred.

#### **10.1.10 Lifestyle factors**

**BACKGROUND:** HD mouse-model studies have shown that rearing mice in an enriched environment delays the onset of symptoms, raising the possibility that pre-symptomatic lifestyle may also affect age-at-onset in humans. Furthermore the age-at-onset of other neurodegenerative disorders such as Alzheimer and Parkinson diseases can be influenced by the type and level of activity regularly undertaken prior to the development of symptoms. A study conducted in Australia and New Zealand showed that avoiding a passive lifestyle may well delay the onset of symptoms of HD. Substantiating these findings may mean that at-risk individuals can be given lifestyle strategies, which if employed from an early age, may lead to symptoms developing several years later than would otherwise be the case.

**AIM:** To examine the link between lifestyle factors and the age at onset of Huntington's disease. The experience and outcome of this retrospective study will inform the development of a cross-sectional prospective study of lifestyle factors with a view to providing individuals at risk of HD with lifestyle strategies that may delay the onset of symptoms.

**STUDY POPULATION:** Manifest HD participants (Stages I and II).

**ASSESSMENT BATTERY:**

- a. Lifestyle Activity Questionnaire: Four sections (Education, Occupation & employment history, Interests & activities, Home duties & activities)
- b. Spirituality: Duke University Religion Index (DUKE)

ASSESSMENT DURATION: 30 minutes.

METHODOLOGICAL APPROACH: For this study a target number of 150-200 participants should provide ample power to detect the effects of a passive lifestyle on age at onset, but it may be possible to observe more subtle effects of intellectual or physical activity with increased numbers.

OUTCOMES: The study is aimed at detecting whether or not lifestyle activities (physical, intellectual and passive) have an impact on the age at onset of HD, independently of the effect of CAG repeat length, and to measure the size of any such impact in a different cohort.

Thirty leisure activities, classified as predominantly physical, intellectual or passive will contribute to total scores for each category of activity within each applicable life stage.

Lifetime average scores (i.e. leisure passivity, leisure intellectuality and leisure physicality scores) will then be generated by averaging the life-stage scores in each category over the nominal pre-morbid lifetime of each individual, defined as (age at onset - 13) years.

Non-leisure activity scores incorporate education, occupation and domestic activity data, again in the categories of physical, intellectual and passive activity. Lifetime average non-leisure scores are the sum of domestic, education and occupation scores within categories. Lifestyle scores comprise the sum of lifetime average leisure and non-leisure scores (within categories).

Relationships between age at onset, CAG repeat length and the various activity parameters will be examined using Pearson correlations followed by a series of linear regression analyses. Because of the known strength of association between CAG repeat length and age at onset, all regression analyses using activity measures as continuous variables will include CAG as a covariate. Where appropriate, different activity scores will be separately entered as variables into fully adjusted multiple logistic regression models. The criterion for significance of association is  $p < 0.05$ . Activity scores will be analysed across tertiles with the mean age at onset (with 95% CIs) calculated for each as a measure of the impact of activity on age at onset.

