HD is a monogenetic disorder with the generational transmission of the disease from parent to offspring, regardless of gender {Huntington, 1872 #16}. The length of the unstable, expanded CAG repeat within the coding region of the HD gene at 4p 16.3 explains many of the genetic features of the disorder, including the variable age at onset, the tendency for juvenile disease to be inherited from fathers, and the (rare) appearance of new mutations [11, 12, 22, 23]. However, the size of the CAG repeat accounts for only about 60-70% of the variance in age at onset and recent studies suggest that other modifier genes may influence age at onset [24]. While the search for modifying genes has been limited thus far to age at onset of motor signs as the phenotype (see e.g. [25, 26]), it is clear that HD displays variability in other features of disease expression, including psychiatric manifestations (e.g., depression, psychosis) and cognitive impairment (e.g., impairment of executive function and/or immediate memory).

Studies of genetic modifiers for outcomes such as disease progression and neuroimaging abnormalities have been hampered by limited availability of high quality prospectively collected longitudinal data. Enroll-HD will provide a information over a wide range of HD phenotypes (e.g., early and late onset, chorea predominant and akinetic/dystonic presentations), including clinical assessments and levels of RNA, protein and metabolites, for studying modifier genes with the goal of identifying and validating therapeutic targets. Further, DNA samples will facilitate genome-wide search for polymorphisms outside the HD gene. Family history data collected as part of Enroll-HD will facilitate assessment of phenotypic variation within families, degree of heritability, and enable sib pair analysis. Thus, the relationships of individual polymorphisms/genes with disease manifestation, progression, and response to treatment can be explored using

genetic association strategies that leverage the combination of enriched phenotypic and genotypic information that will be collected in Enroll-HD.

The goal of Enroll-HD is to build a large and rich database of clinical information and biospecimens that will serve as a basis for future studies aimed at developing tools and biomarkers for progression and prognosis, identifying clinically relevant phenotypic characteristics, and establishing clearly defined endpoints for interventional studies.

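### Lifestyle sub-study: mean age at onset by activity tertile is offered as a measure of impact with no CAG adjustment stated, although the aim is the size of a CAG-independent effect

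*Protocol*

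**What the plan says.** Everything here is in Protocol 10.1.10 unless stated otherwise.

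- **Aim.** The sub-study asks whether lifestyle activities "have an impact on the age at onset of HD, independently of the effect of CAG repeat length, and to measure the size of any" effect found.
- **Main analysis.** Relationships between age at onset, CAG and the activity parameters "will be examined using Pearson correlations followed by a series of linear regression analyses".
- **CAG rule.** Because the CAG association is known to be strong, "all regression analyses using activity measures as continuous variables will include CAG as a covariate".
- **Logistic models.** Where appropriate, "different activity scores will be separately entered as variables into fully adjusted multiple logistic regression models". No binary outcome or cut-point is named.
- **Tertiles.** "Activity scores will be analysed across tertiles with the mean age at onset (with 95% CIs) calculated for each", and this serves "as a measure of the impact of activity on age at onset". No covariate is mentioned for these means.
- **Size.** The target is 150-200 participants, said to be ample for detecting effects of a passive lifestyle. No effect size, SD or power figure is given.

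Section 2 adds that "the size of the CAG repeat accounts for only about 60-70% of the variance in age at onset".

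**The concern.** The aim has two parts: to detect a CAG-independent effect and to size it. The tertile means are the output that the text explicitly labels a measure of impact. They would be in years, so they are also the result most easily carried forward. Yet the adjustment rule is worded for regressions on continuous scores, and a mean per tertile is neither of those. The reason given for adjusting, the strength of the CAG association, applies to tertiles just as much.

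Two things are at stake. Leaving out the strongest known predictor makes the tertile intervals wider than they need be. And if activity scores correlate with CAG at all, part of any gap between tertiles reflects CAG and not lifestyle. The background to 10.1.10 looks ahead to lifestyle strategies for people at risk, so a figure in years of delayed onset should not mix the two.

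The logistic models are a smaller matter. Age at onset is continuous, so the reader cannot tell what they would model.

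**Working it through.** **The plan's own figure.** The 150-200 target cannot be reproduced, because no effect size, SD or power is stated. What the planned CAG-adjusted regression could detect can be worked out (two-sided 0.05 assumed, one covariate, Fisher z):

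smallest partial r = tanh[(1.960 + z_power) / √(N − 4)]

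- N = 150: 0.228 at 80% power, 0.262 at 90%.
- N = 200: 0.197 at 80% power, 0.227 at 90%.

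**Inputs for the tertile means.** R² for CAG = 0.60-0.70 (Section 2). N = 150-200 (10.1.10), so 50 to about 67 per tertile. Assumed, because no document gives them: SD of age at onset 10 years; activity-CAG correlation ρ from 0 to 0.3; normal variables; the Section 2 R² applies to the sub-study's Stage I-II participants.

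**Step 1: precision.** The residual SD after adjustment is √(1 − R²) of the raw SD.

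- R² = 0.60: √0.40 = 0.632, and 1/0.40 = 2.5 times the sample.
- R² = 0.70: √0.30 = 0.548, and 1/0.30 = 3.3 times the sample.

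For one tertile mean, the 95% half-width is 1.96 × SD/√n:

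| n per tertile | Raw (years) | Adjusted, R² = 0.60 | Adjusted, R² = 0.70 |
|---|---|---|---|
| 50 | 1.96 × 10/√50 = 2.77 | 1.75 | 1.52 |
| 66.7 | 1.96 × 10/√66.7 = 2.40 | 1.52 | 1.31 |

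This ignores the small penalty for estimating the CAG slope and for CAG imbalance between tertiles.

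**Step 2: confounding with no CAG-independent effect.** The outer thirds of a standard normal have means of ±1.091, so the size of the raw top-bottom gap is

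2 × 1.091 × ρ × √R² × SD

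| ρ | R² = 0.60 | R² = 0.70 |
|---|---|---|
| 0 | 0 | 0 |
| 0.1 | 1.7 years | 1.8 years |
| 0.2 | 3.4 years | 3.7 years |
| 0.3 | 5.1 years | 5.5 years |

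A simulation of 2 million draws per setting agrees: 0.17-0.18, 0.34-0.36 and 0.51-0.55 SD at ρ = 0.1, 0.2 and 0.3.

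**Step 3: behaviour at the planned size.** This used 3,000 simulated studies per setting, at N = 150 and 200 and R² = 0.60 and 0.70. The plan specifies no test between tertiles; a t-test of top against bottom was imposed for illustration.

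- *No independent effect.* The CAG-adjusted regression rejected in 4.0-5.3% of runs at every ρ tried. The raw tertile contrast rejected in 4-5% at ρ = 0, 38-56% at ρ = 0.2 and 72-89% at ρ = 0.3.
- *Assumed independent effect of 0.15 SD.* Power was 79-97% for the adjusted regression and 5-47% for the raw contrast. In this set-up the confounding ran against the effect; with the opposite sign it would inflate the contrast.

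**The case against.** The strongest reply is that the plan already contains the right analysis. The same paragraph requires CAG in every regression on a continuous activity score. That tests the independent effect, and the slope gives its size. This stands, and Step 3 supports it. A reader might infer that the sub-study cannot show a CAG-independent effect; the text contradicts that.

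Second, the tertile means are called a measure of impact, not the primary or only one, and the text does not say they are unadjusted. That also stands in part. The lack of adjustment is read from silence together with a rule limited to continuous scores. A tertile display beside adjusted regressions is ordinary practice when it is labelled descriptive, but here it is presented as a measure of impact.

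Third, 10.1.10 is an outline, and Sections 5.4.7 and 6.2 foresee a data analysis plan for each sub-study. This lowers the severity. It does not remove the point, because the outline states a method that fits its aim poorly and the later plan may inherit it.

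Fourth, the logistic models are optional and described as fully adjusted, and the text does not tie them to age at onset. A reader might infer that onset will be cut at an arbitrary age. The document does not say so, and what remains is an undefined outcome.

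A reader might also infer a multiplicity failure from several scores judged at p < 0.05. The total scores are sums of the leisure and non-leisure scores, so counting all of them as independent tests would overstate it. The work is retrospective and meant to inform a later study. I do not raise this.

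**Conclusion.** The point holds in a limited form. The planned regressions can estimate a CAG-independent effect. The tertile means, as written, are a second measure of impact that does not match the aim.

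The loss of precision rests on the protocol's own 60-70%: adjusted intervals would be about 55-63% as wide, provided that figure carries over to Stage I-II participants. The confounding is conditional. It is nil if activity and CAG are uncorrelated, and reaches about 5 years between top and bottom tertiles at an assumed correlation of 0.3 and an assumed SD of 10 years. Nothing in the document says where in that range the truth lies.

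This is a should-fix point. The undefined logistic outcome is a minor clarification within it.

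One limit applies to any remedy. Leisure scores are averaged over a span of (age at onset − 13) years, so the outcome enters the exposure. CAG adjustment does not remove that separate problem.

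**What to change.** In 10.1.10, and in the sub-study's own analysis plan:

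1. Report mean age at onset by activity tertile as CAG-adjusted least-squares means with 95% CIs, from a linear model with tertile and CAG.
2. Name the CAG-adjusted linear coefficient as the main measure of effect size.
3. Label any raw tertile means as descriptive.
4. Delete the logistic models, or state the binary outcome they are for.
5. Address the dependence of the leisure scores on age at onset separately.

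Items 1-4 change wording only. Research genotyping is already a core assessment (Table 1 and Section 5.2.5), so they need no new data, visits or participants. Item 5 needs separate thought about how the scores are built.
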